#### 4.6.3. Exploratory Analyses

Analyses for the exploratory endpoints will be conducted using the FAS and PP populations.

Exploratory endpoints include:

- Mean change in histological score from baseline to Week 12 (Day 84)
- Effects of ADA on PK, safety, and efficacy in subjects with positive ADA

For the first two exploratory endpoints, these will be analyzed in the same fashion as their primary and secondary counterparts. The effects of ADA on PK, safety, and efficacy may be evaluated by performing subgroup analyses (ADA + vs. ADA -) if ADA is detected in clinical samples.

## 4.7. Pharmacokinetic and Pharmacodynamic Evaluations

Pharmacokinetic analyses will be conducted using the Pharmacokinetic Population. Pharmacodynamic analyses will be conducted using the FAS and PP populations.

### 4.7.1. Pharmacokinetic Evaluations

Pharmacokinetic variables will be calculated from the individual PTG-100 plasma concentration data using standard non-compartmental methods. Maximum concentration ( $C_{\max}$ ), trough (predose) concentration ( $C_{\text{trough}}$ ) and the time of  $C_{\max}$  ( $T_{\max}$ ) will be taken directly from the observed data. The area under the concentration-time curve ( $AUC_{0-t}$ ) from time 0 to the time of the last sample collection will be calculated using the linear trapezoidal rule.

PK analyses will be performed using commercial software such as Phoenix™ WinNonlin® Version 6.4 or higher (Certara USA Inc.). All pharmacokinetic calculations will be performed using published non-compartmental relationships. Actual dose administration times and sample collection times will be used for the analyses as recorded on the CRF. Plasma concentrations below the lower limit of quantification will be set to zero for the analysis.

Individual PTG-100 concentration data will be listed and summarized by treatment group with descriptive statistics (sample size [N], arithmetic mean, standard deviation [SD], median, minimum, maximum, geometric mean, and geometric coefficient of variation [CV]). Mean and individual PTG-100 concentration-time profiles will be presented graphically on both linear and semi-logarithmic scales. All statistical analyses will use non-rounded parameter estimates. Plasma concentration data and the pharmacokinetic parameter estimates will be presented by study group. Pharmacokinetic parameter estimates will be three or four significant figures for presentation. No attempt will be made to estimate missing data. Other parameters and data handling procedures may be added as appropriate. Missing values will not be imputed, and if sufficient data are missing for a given subject, that subject may be considered non-evaluable for pharmacokinetic analysis and would not be included in the PK Population.

All plasma concentration data and the per-subject pharmacokinetic parameters will be displayed in listings.

#### 4.7.2. Pharmacodynamic Evaluations

Quantitation of  $\alpha 4\beta 7$  %RO and  $\alpha 4\beta 7$  RE on peripheral blood T cells will be evaluated as secondary endpoints.

Exploratory endpoints will include:

1. Analysis of peripheral blood lymphocytes in subjects on individual PTG-100 dose levels to placebo
2. Average number of  $\beta 7$  positive cells in colonic biopsies as assessed by immunohistochemistry (IHC) in subjects by PTG-100 dose levels and compared to placebo
3. Characterization of immunologic biomarkers in the target population (selected sites only)

Individual data will be listed for each individual and summarized by nominal sampling time point and treatment group with descriptive statistics (arithmetic mean, SD, median, minimum, and maximum). A summary of change-from-baseline at each protocol specified time-point by treatment group will also be presented. The change of PD indicators over time will be demonstrated graphically and will be compared among the dose levels using the same mixed model as the other continuous secondary and exploratory endpoints.

Further summaries may use pre-clinical and clinical data from previous studies to explore the PK/PD relationship to correlate with clinical endpoints.

Receptor occupancy and  $\alpha 4\beta 7$  expression in peripheral blood will be listed for each individual and summarized by treatment group using frequency/count data.

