#### 4.2.8. Missing, Unused, and Spurious Data

All data recorded on the CRF will be included in data listings that will accompany the clinical study report.

For the primary efficacy endpoint and other success/failure secondary endpoints, subjects who discontinue prior to Week 12 will be considered treatment failures, a worst-case scenario.

These endpoints include

- Clinical Remission (primary endpoint)
- Clinical Response
- Endoscopic Response
- Endoscopic Remission

A single sensitivity analysis on each of these endpoints will utilize the per protocol population (complete-case) in order to examine the robustness of the results.

For all continuous secondary endpoints, data will be analyzed using a mixed model repeated measures approach described in Section 4.6.2. The MMRM method assume that missing data arose from a missing at random (MAR) mechanism, i.e. the missing data is independent of unobserved data given the non-missing data. The MAR assumption is reasonable in clinical trials as the observed data explain much of the missingness in many scenarios, particularly in well controlled studies such as clinical trials, in which an extensive effort is made to observe all the outcomes and the factors that influence them. In MMRM, the information from the observed data is used via the within-patient correlation structure to provide information about unobserved data. The data from all visits are simultaneously analyzed using restricted maximum likelihood methods and no explicit imputation for missing values is performed. This method will be used in the testing of the secondary endpoints.

In addition, sensitivity analyses may be performed on complete datasets where missing data is imputed using the following methodology:

- LOCF (last observation carried forward)
- WOCF (missing data imputed using the worst observation observed prior to that time point)
- Per Protocol population (complete-case scenario- no imputation required)
- Multiple Imputation

For multiple imputation, two approaches may be used. In the first approach, for missing response data at various time points, the following steps are taken:

- Draw a random sample from the normal distribution with a mean and variance calculated from the non-missing responses at that time point
- Repeat this process five times to form five imputed complete datasets
- Fit the MMRM model to each imputed dataset to estimate the treatment effect on the response variable and the variance

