- Combine the results from the five imputed dataset using SAS Proc MIANALYZE to derive the multiple imputation estimates of treatment effect and variance.

The second multiple imputation approach will be used to impute data in the event that missing data are missing not at random (MNAR) but rather depend on the observed and unobserved data. This imputation approach would use the same steps as above, but the random sample would be drawn from a distribution pre-defined and related to the responses that are observed.

Exploratory endpoints will not be imputed.

Adverse event (AE) dates that are missing or incomplete will be handled in the following manner to determine whether an AE is treatment-emergent:

If the start date/time of an AE is partially or completely missing, the date/time will be compared as far as possible with the date/time of the start of administration of study drug. The AE will be assumed to be treatment emergent if it cannot be definitively shown that the AE did not occur or worsen during the treatment-emergent period (worst case approach).

The following general rules will be used:

- If the start time of an AE is missing but the start date is complete, an AE will only be excluded as being treatment emergent if the start date is before the date of study drug administration or if the stop date/time is before study drug administration.
- If the start time and day are missing but the start month and year are complete, an AE will only be excluded as being treatment emergent if the start month/year is before the month/year of study drug administration or if the stop date/time is before study drug administration.
- If the start day and month are missing but the start year is complete, an AE will only be excluded as being treatment emergent if start year is before the year of study drug administration or if the stop date/time is before study drug administration.
- If the start date is completely missing, an AE will be considered treatment-emergent unless the stop date/time is before study drug administration.

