**Table 1 Evaluation Intervals for Efficacy Analysis**

Evaluation	Protocol-Specified Interval	Interval for Analysis
Baseline (Screening and Pre-Dose)	Day -35 to Day 0	Day -35 to Day 0 (Pre-Dose)
Day 0 (Post-Dose)	Day 0 (Post-Dose)	Day 0 (Post-Dose)
Day 14	Day 11 post to Day 17 post	Day 1 post to Day 24 post
Day 28	Day 25 post to Day 31 post	Day 25 post to Day 38 post
Day 42	Day 39 post to Day 45 post	Day 39 post to Day 52 post
Day 56	Day 53 post to Day 59 post	Day 53 post to Day 66 post
Day 70	Day 67 post to Day 73 post	Day 67 post to Day 80 post
Day 84	Day 81 post to Day 87 post	Day 81 post to Day 104 post
Day 112 (Follow-Up)	Day 105 post to Day 119 post	Day 105 post to Day 119 post

Actual dates and times will be used for pharmacokinetic and pharmacodynamic analyses rather than nominal days and times.

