#### 4.6.2. Secondary Efficacy Analyses

Analyses for the secondary endpoints will be conducted using the FAS and PP populations. Where applicable, baseline is defined as the last non-missing pre-treatment assessment prior to initiation of study treatment.

All secondary endpoints that reflect a dichotomous response will be analyzed in the same manner as the primary efficacy endpoint. These secondary endpoints include

- Proportion of subjects with endoscopic response at Week 12 (Day 84) (defined as an endoscopic subscore of 0 or 1)
- Proportion of subjects with clinical response at Week 12 (Day 84) (defined as at least 1 point and 30% reduction from baseline in rectal bleeding and stool frequency subscores)
- Proportion of subjects developing neutralizing antidrug antibodies (ADA)
  - Methods for detection of ADA in clinical samples are presented in Section 7.8 of the protocol
- Proportion of subjects with endoscopic remission at Week 12 (defined as an endoscopic subscore of 0)

Hypothesis testing for all continuous secondary endpoints will be conducted using repeated measures mixed analysis of covariance model adjusted for treatment, time point, treatment-by-time point interaction, stratification factor (TNF-alpha prior use) and baseline values. For subjects who withdraw prematurely, the last observation will be carried forward. These analyses will be based on the Stage 1 and Stage 2 combined data for exploratory purposes. Pairwise comparisons of active drug versus placebo for the change from baseline endpoints will be conducted and p-values derived as described in the analysis of the primary efficacy endpoint. In addition, a summary of observed values and change from baseline values will be presented for each endpoint. Graphical summaries by treatment group of mean change from baseline over time up to Week 12 will also be presented.

Continuous secondary endpoints include

- Mean change in complete Mayo Score (including all four subscores) from baseline to Week 12
- Mean change in Partial Mayo Score (excluding endoscopy subscore) from baseline to Weeks 2, 4, 6, 8, 10, 12, and 16 (Days 14, 28, 42, 56, 70, 84, and 112)
- Mean change in endoscopy subscore from baseline to Week 12 (Day 84)
- Mean change in rectal bleeding and stool frequency subscores from baseline to Weeks 2, 4, 6, 8, 10, 12, and 16 (Days 14, 28, 42, 56, 70, 84, and 112)
- Mean change in fecal calprotectin levels from baseline to Weeks 6 and 12

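### SAP 4.7.2 borrows a mixed model with two conflicting missing-data rules; under the carry-forward rule an off-drug Early Termination sample can stand as Week 12 receptor occupancy or expression (minor)

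*SAP*

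**What the plan says.** SAP 4.7.2 names RO and RE on peripheral blood T cells as secondary endpoints. Change in the PD indicators "will be compared among the dose levels using the same mixed model as the other continuous secondary and exploratory endpoints". The section has no missing-data sentence of its own.

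The SAP describes the borrowed model in two places:

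- **SAP 4.6.2**, where the model is set out: "For subjects who withdraw prematurely, the last observation will be carried forward".
- **SAP 4.2.8**: MMRM by restricted maximum likelihood, with no explicit imputation. "This method will be used in the testing of the secondary endpoints". Carry-forward appears there only among optional sensitivity analyses. The section adds "Exploratory endpoints will not be imputed", which does not settle the matter because RO and RE are labelled secondary.

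For pharmacokinetics, SAP 4.7.1 is explicit: "Missing values will not be imputed". There is no PD counterpart.

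On timing, SAP 4.2.9 says "Actual dates and times will be used for pharmacokinetic and pharmacodynamic analyses rather than nominal days and times", while SAP 4.7.2 has PD data "summarized by nominal sampling time point and treatment group". The analysis windows in 4.2.9 are for efficacy variables.

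On sampling, Protocol Table 6-1 schedules a PD sample at Early Termination, with no study-drug administration marked for that visit. Protocol 6.8 allows the visit up to 10 days after drug is stopped. PD analyses use the full analysis set and per-protocol population (SAP 4.7), and neither definition limits samples by time since last dose.

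**The concern.** Two statisticians could each follow the SAP faithfully and report different Week 12 RO and RE results. One would carry an Early Termination value forward to Week 12; the other would not impute. If that value was drawn days after the last dose, the first analysis reports partly washed-out occupancy as if it belonged to the assigned dose.

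RO and RE are the target-engagement evidence read alongside the dose-response objective. Dilution would matter most if stopping differed between doses. That is plausible, since Protocol 6.8 takes subjects off study drug when a flare needs prohibited rescue. Unequal dilution could look like a dose difference, and added spread could hide a real one.

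**Working it through.** **Documented inputs.** RO and RE are secondary (SAP 4.7.2). The two missing-data rules are in SAP 4.6.2 and 4.2.8. Early Termination is up to 10 days after stopping (Protocol 6.8). Sustained RO and saturated RE were seen 24 hours after dosing in Phase 1 (Protocol 2.3).

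**Assumed inputs.** The documents give no stopping rate, RO or RE level, SD, washout beyond 24 hours or number of PD subjects (PD is collected at selected sites only). I take:

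- r = share of an arm whose last PD value is off drug, 5-20%. Subjects dosed at Early Termination, or with no sample there, do not count.
- L = share of the drug effect lost by that sample, 0-100%.
- RO mean 70 and SD 12; RE effect 40 and SD 20; 20 or 40 PD subjects per arm.

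The range for L is wide because washout is unknown. If the effect decays with half-life h over a gap g, L = 1 - 2^(-g/h). At g = 5 days and h = 1, 3 or 7 days, L is 97%, 69% or 39%. If the effect persists, L is near 0.

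**Step 1: carry-forward (4.6.2).** Week 12 mean = true mean x (1 - r x L). The relative shortfall runs from 0 (L = 0) to 0.20 x 1.00 = 20%. At RO 70, r = 10% and L = 50%: 70 x (1 - 0.05) = 66.5.

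**Step 2: no imputation (4.2.8).** The off-drug value enters at its nearest visit and affects Week 12 only through within-subject correlation. I simulated five trough visits (Days 14, 28, 42, 56, 84), with the off-drug value at Day 28, 42 or 56 and later visits missing. The model had arm-by-visit means and unstructured covariance. At the extreme (r = 20%, L = 100%) and correlations 0.3, 0.5 and 0.7, the Week 12 means are 67.2, 66.2 and 65.5. Shortfalls are (70 - 67.2)/70 = 4.0%, (70 - 66.2)/70 = 5.4% and (70 - 65.5)/70 = 6.4%. Carry-forward in the same setting gives about 56, that is 20%.

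**Step 3: Early Termination as its own nominal time point.** The value never enters a scheduled visit, so the shortfall is 0.

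**Step 4: effect on a dose comparison** (2,000 simulated trials per setting, correlation 0.5, two-sided 5%; stratum and baseline terms not simulated).

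| Quantity | Rule | L=0 | 25% | 50% | 100% |
|---|---|---|---|---|---|
| Mean RO, true 70, r=10% | carry-forward | 70.0 | 68.2 | 66.4 | 63.0 |
| | no imputation | 70.0 | 69.5 | 69.0 | 68.2 |
| False RO difference, r 5% vs 15%, 40/arm | carry-forward | 5% | 10% | 16% | 25% |
| | no imputation | 6% | 6% | 6% | 10% |
| | off-drug values removed | 6% | 5% | 5% | 5% |
| Power, 10-point RO difference, r=10% in both arms, 20/arm | carry-forward | 73% | 65% | 50% | 26% |
| | no imputation | 71% | 68% | 68% | 59% |

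With off-drug values removed, power in the last setting is 69-71%, against 72-75% if everyone stays on drug. Monte Carlo standard error is about 0.5 points near 5% and 1 point near 70%.

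For RE at 40 per arm, the false-difference rate is 5/5/7/14% under carry-forward and 4-5% without imputation.

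**Hand check of the 25%.** At L = 100% the mean difference is 70 x (0.15 - 0.05) = 7.0. Variances are 0.95 x 144 + 0.05 x 0.95 x 4900 = 369.6 and 0.85 x 144 + 0.15 x 0.85 x 4900 = 747.2. The standard error is sqrt((369.6 + 747.2)/40) = 5.28, so z = 1.33 and the rejection probability is about 26%.

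**The case against.** The strongest reply is that 4.2.8 is the better reading. SAP 4.7.2 borrows a model, not an imputation rule. The carry-forward sentence sits under secondary efficacy analyses, and neither the endpoint list there nor the list in Protocol 7.4 includes RO or RE. On that reading the results up to L = 50% are within a point or so of Monte Carlo error from those under the fix, and only near-total loss of effect separates them. This stands, and it is why the point is minor. It does not remove the point: 4.6.2 applies its model, carry-forward included, to continuous secondary endpoints without excluding PD.

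Second, Early Termination has its own column in the schedule, so summarising by nominal time point may keep it apart. That is a natural reading, but the SAP does not state it, and 4.2.9 points to actual times instead. If the efficacy windows were applied to PD, a last dose on Days 71-80 could put an Early Termination sample in the Day 84 window (81-104) with no carry-forward at all.

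Third, some Early Termination samples will be on drug. Protocol 6.8 is headed as the final treatment day, and footnote 17 to Table 6-1 foresees postdose samples there if possible. This stands: an off-drug value is possible, not certain.

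Fourth, dropping off-drug values conditions on a post-randomisation event, and analysing all observed values by assigned dose is defensible. This also stands; such an analysis has a place as a sensitivity analysis.

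A reader might also infer that RE saturation at 300 mg in Phase 1 makes a false 300 versus 900 mg difference in RE likely. The calculations do not bear that out: there is no inflation without imputation, and at most 7% under carry-forward up to L = 50%.

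**Conclusion.** The concern holds as a minor defect. Two stated rules conflict for RO and RE, and the one in 4.6.2 can report an off-drug Early Termination value as Week 12 RO or RE of the assigned dose. The relative shortfall is r x L, 0 to 20% under the assumed ranges. Under 4.2.8 it is 0 to about 6% and negligible unless most of the drug effect is lost; it is zero if Early Termination is a separate time point. Every size here rests on assumed stopping, washout, variability and PD numbers, and no effect at all (L = 0) lies within the range.

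A reader might take the 25% false-difference rate as the expected damage. It needs carry-forward, complete loss of effect and threefold unequal stopping together, and the documents establish none of these for PD. Nor do they support extending the point to the trial's conclusions. RO and RE are outside the primary test and the ten hierarchical secondary endpoints (SAP 2.5.1, 4.2.5), and SAP 4.6.2 calls its combined-stage continuous analyses exploratory. The documents do not say that interim dose selection uses the 4.7.2 model. What is exposed is the exploratory PD dose comparison and the PK/PD reading built on it.

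**What to change.** In SAP 4.7.2, before unblinding, state that:

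1. RO and RE are analysed by MMRM without carry-forward; 4.2.8 governs, not the carry-forward sentence in 4.6.2.
2. PD samples taken more than a pre-specified interval after the last dose (for example one dosing interval, since sustained RO is reported at 24 hours) are listed by time since last dose. They are left out of the on-treatment model and the nominal-visit summaries.
3. An analysis of all observed values may be kept as a sensitivity analysis.

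No visits or samples are added. The times needed are already recorded; for PK, SAP 4.7.1 says "Actual dose administration times and sample collection times will be used for the analyses as recorded on the CRF". As an optional clarification, Protocol 6.8 and footnote 17 to Table 6-1 could say that postdose samples at Early Termination are taken only if a dose is given that day.

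The costs are that slightly fewer subjects contribute a Week 12 value (simulated power 69-71% against 72-75% with all on drug, at 20 per arm), and that the cut-off has no documented washout basis beyond 24 hours.

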## 4.8. Safety Analyses

Safety analyses will be conducted using the Safety Population. The safety analyses generated will be a presentation of AEs, SAEs, clinical labs, vital signs, ECGs, and physical examinations as described below.

### 4.8.1. Adverse Events

The primary safety endpoint is the proportion of subjects with at least 1 AE comparing individual PTG-100 dose groups with placebo.

Secondary endpoints (all based on comparison of individual PTG-100 dose levels to placebo) will include:

- Frequency and type of AEs (affecting  $\geq 5\%$  of subjects)
- Proportion of subjects with at least 1 SAE
- Number and type of SAEs
- Frequency of adverse events of special interest (AESI) including serious or opportunistic infection (viral, bacterial, fungal including systemic/ gut localization), allergic/ drug reactions, immune system disorders, and PML or new onset neurologic symptoms

Adverse events will be coded using the Medical Dictionary for Regulatory Activities (MedDRA) and displayed in tables and listings using System Organ Class (SOC) and Preferred Term.

Analyses of adverse events will be performed for those events that are considered treatment emergent, where treatment emergent is defined as any adverse event with onset after the administration of study medication through the end of the study visit or any event that was present at baseline but worsened in intensity or was subsequently considered drug-related by the investigator through the end of the study.

Adverse events are summarized by subject incidence rates, therefore, in any tabulation, a subject contributes only once to the count for a given adverse event (SOC or preferred term).

The number and percentage of subjects

- with any treatment-emergent adverse event
- with any treatment-emergent adverse events assessed by the Investigator as related to treatment (definite, probable, or possible relationship)
- with any treatment-emergent serious adverse event
- with treatment-emergent adverse events by severity
- with adverse events affecting  $\geq 5\%$  of subjects within any treatment group across both stages of the study
- with AESI

will be summarized by treatment group and overall. In addition, all active groups will be pooled in the summaries for comparison to placebo. In these tabulations, each subject will contribute

only once (i.e., the most related occurrence or the most intense occurrence) to each of the incidence rates in the descriptive analysis, regardless of the number of episodes.

Three additional tables will present the incidence of treatment-emergent adverse events by PT, treatment-emergent events leading to study withdrawal and treatment-emergent events with a fatal outcome, sorted in the order of frequency for the entire safety population.

All adverse events occurring on study (pre-treatment, treatment, follow-up) will be listed in subject data listings.

By-subject listings also will be provided for the following: subject deaths; serious adverse events; and adverse events leading to withdrawal.

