7.5 Statistical Analysis of Safety Data

The primary safety endpoint is the proportion of subjects with at least 1 AE comparing individual PTG-100 dosing groups with placebo.

The secondary endpoints (all based on comparison of individual PTG-100 dose levels to placebo) will include:

1. Frequency and type of AEs (affecting $\geq 5\%$ of subjects)
2. Proportion of subjects with at least 1 SAE
3. Number and type of SAEs
4. Frequency of AEs of special interest including serious or opportunistic infection (viral, bacterial, fungal including systemic/gut localization), allergic/drug reactions, immune system disorders, and suspected PML
5. Clinically significant changes in safety labs, ECGs, or physical examination findings (including vital signs).

Continuous safety data will be summarised with descriptive statistics (arithmetic mean, standard deviation [SD], median, minimum, and maximum) by dose level. Categorical safety data will be summarised with frequency counts and percentages by dose level. Adverse events will be coded using the most current Medical Dictionary for Regulatory Activities available, which will be indicated in the Data Management Plan. A by-participant AE data listing, including verbatim term, preferred term, system organ class, treatment, severity, and relationship to study drug, will be provided. The number of participants experiencing treatment-emergent AEs (TEAEs) and number of individual TEAEs will be summarised by treatment group, system organ class, and preferred term. The TEAEs will also be summarised by severity and by relationship to study drug.

Laboratory evaluations, vital signs assessments, and ECG parameters will be summarised by treatment group and protocol-specified collection time point. A summary of change-

from-baseline at each protocol-specified time point by treatment group will also be presented.

Clinically significant changes in physical examinations will be listed for each participant and described in the text of the Clinical Study Report.

Medical history will be listed by subject.

Concomitant medications will be listed by participant and coded using the most current World Health Organization drug dictionary.

Further details regarding presentation and analysis of safety data will be detailed in the SAP.

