## **5. CHANGES TO PLANNED ANALYSES**

As of this date, there have been no changes between the protocol-defined statistical analyses and those presented in this statistical plan.

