Table 14.2.2.7A	Change in IBDQ score from Baseline Over Time (FAS)
Table 14.2.2.7B	Change in IBDQ score from Baseline Over Time (PP)

Table 14.2.2.7C	Change in IBDQ score from Baseline Over Time (Sensitivity Analyses – if Needed)
Table 14.2.2.7A	Change in Histological score from Baseline Over Time (FAS)
Table 14.2.2.7B	Change in Histological score from Baseline Over Time (PP)
Table 14.2.3	Summary of Pharmacokinetic Parameters (PK Population)
Table 14.2.4.1A	Change in $\alpha 4\beta 7$ Receptor Occupancy on Peripheral Blood T cells Over Time (FAS)
Table 14.2.4.1B	Change in $\alpha 4\beta 7$ Receptor Occupancy on Peripheral Blood T cells Over Time (PP)
Table 14.2.4.2A	Summary of $\alpha 4\beta 7$ Receptor Expression on Peripheral Blood T cells Over Time (FAS)
Table 14.2.4.2B	Summary of $\alpha 4\beta 7$ Receptor Expression on Peripheral Blood T cells Over Time (PP)
Table 14.2.4.3A	Change in Peripheral Blood Lymphocytes Over Time (FAS)
Table 14.2.4.3B	Change in Peripheral Blood Lymphocytes Over Time (PP)
Table 14.2.4.4A	Change in $\beta 7$ Positive Cells in Colonic Biopsies Over Time (FAS)
Table 14.2.4.4B	Change in $\beta 7$ Positive Cells in Colonic Biopsies Over Time (PP)
Table 14.2.5.1A	Proportion of Subjects with Positive Neutralizing ADA by Week 12 and Week 16 (FAS)
Table 14.2.5.1B	Proportion of Subjects with Positive Neutralizing ADA by Week 12 and Week 16 (PP)

*Displays of Adverse Events (CSR Section 14.3.1)*

Table 14.3.1.1	Overall Summary of Treatment-Emergent Adverse Events by Treatment Group (Safety)
Table 14.3.1.2	Summary of Treatment-Emergent Adverse Events by System Organ Class, Preferred Term and Treatment Group, Sorted in Descending Frequency according to the Total Column (Safety)

Table 14.3.1.3	Summary of Related/Possibly, Probably and Definitely Related Treatment-Emergent Adverse Events by System Organ Class, Preferred Term and Treatment Group (Safety)
Table 14.3.1.4	Summary of Treatment-Emergent Adverse Events by Severity, System Organ Class, Preferred Term and Treatment Group (Safety)
Table 14.3.1.5	Summary of Treatment-Emergent Serious Adverse Events by System Organ Class, Preferred Term and Treatment Group (Safety)
Table 14.3.1.6	Summary of Most Common ( $\geq 5\%$ within any treatment group) Treatment-Emergent Adverse Events by System Organ Class, Preferred Term and Treatment Group (Safety)
Table 14.3.1.7	Summary of Treatment-Emergent Adverse Events by Preferred Term and Treatment Group (Safety)

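### Under SAP 4.8.1's once-per-subject rule, no planned table gives by arm the number of individual TEAEs or the number of SAEs that the protocol calls for.

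*SAP*

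**What the plan says.** Protocol 7.5, repeated in the synopsis, commits to two TEAE summaries: the number of participants with TEAEs, and the "number of individual TEAEs will be summarised by treatment group, system organ class, and preferred term". Its secondary safety endpoints, each a comparison of individual dose levels with placebo, include both the proportion of subjects with an SAE and the number and type of SAEs.

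SAP 4.8.1 carries over both SAE endpoints as separate items: "Proportion of subjects with at least 1 SAE" and "Number and type of SAEs". It then sets the counting unit:

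- "Adverse events are summarized by subject incidence rates", and therefore "in any tabulation, a subject contributes only once to the count for a given adverse event (SOC or preferred term" (closing parenthesis omitted).
- In the number-and-percentage summaries that follow, a subject contributes once "to each of the incidence rates in the descriptive analysis, regardless of the number of episodes".

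SAP 7.1 names one summary table for SAEs, Table 14.3.1.5. No table title there refers to a count of events. SAP 5 states that "there have been no changes between the protocol-defined statistical analyses and those presented in this statistical plan".

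**The concern.** The protocol distinguishes how many subjects had an event from how many events occurred. The SAP keeps an endpoint of the second kind but gives a counting rule that produces only the first. Protocol 7.9 says the tables will be programmed from the final SAP, so a programmer who follows 4.8.1 to the letter would leave the event counts out. Nobody would be alerted, because SAP 5 reports no departure, although SAP 1.2 says the SAP will set out differences from the protocol.

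At stake is a by-arm summary that the protocol requires, and half of a named secondary safety endpoint. Two arms with the same number of affected subjects would look alike in the tables even if one had more repeat episodes. Safety and tolerability is a primary objective, and Protocol 2.2 describes this as the first use of the drug in subjects with UC.

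**Working it through.** The documents give no AE or SAE rate and no event count, so there is no stated figure to reproduce. The main check compares the texts. The arithmetic after it only shows scale, under assumed rates.

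**Step 1: what is promised and what is planned**

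| Item | Promised | SAP 4.8.1 and 7.1 |
|---|---|---|
| Participants with TEAEs, by arm, SOC, preferred term | Protocol 7.5 | Produced |
| Individual TEAEs, by arm, SOC, preferred term | Protocol 7.5 | No table or column named |
| Proportion of subjects with an SAE | Protocol 7.5, SAP 4.8.1 | Produced |
| Type of SAEs by arm | Protocol 7.5, SAP 4.8.1 | Produced (Table 14.3.1.5, by SOC and preferred term) |
| Number of SAEs by arm | Protocol 7.5, SAP 4.8.1 | No table or column named |

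**Step 2: what the rule removes**

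SAP 4.8.1 contains two sentences of different scope. The first covers every tabulation and works per SOC or preferred term. The second covers the number-and-percentage summaries and each incidence rate in them. A subject with two different preferred terms therefore counts in both preferred-term rows. Two things are lost: repeats of the same term, and multiple terms within one SOC at the SOC row.

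Hypothetical example: a subject has two SAEs coded to one UC-flare term and one SAE coded to an infection term in another SOC. This subject has 3 SAEs.

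- Overall SAE row: adds 1.
- Flare term row: adds 1 (2 episodes occurred).
- Infection term row: adds 1 (1 episode occurred).

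Both types are visible, and at preferred-term level only the second flare is missing.

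**Step 3: scale**

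For any row with E episodes in S subjects, the shortfall is 1 − S/E, or 1 − 1/r with r = E/S episodes per affected subject. At a preferred-term row, r counts repeats of that same term only.

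Inputs: n = 75 subjects per arm, the middle of the 70 to 80 given in SAP 2.1 for selected doses; m = mean episodes per subject for the row, assumed. Expected events are n × m. Expected subjects with at least one event are:

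- Independent episodes (Poisson): n × (1 − e^(−m)).
- Episodes clustered within subjects (negative binomial, k = 0.5, assumed): n × (1 − (k/(k+m))^k).

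For example, at m = 0.5 there are 75 × 0.5 = 37.5 events. The Poisson subject count is 75 × (1 − e^(−0.5)) = 29.5, so the shortfall is 1 − 29.5/37.5 = 21%.

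| m | Events | Subjects, Poisson | Shortfall | Subjects, clustered | Shortfall |
|---|---|---|---|---|---|
| 0.05 | 3.8 | 3.7 | 2.5% | 3.5 | 7% |
| 0.1 | 7.5 | 7.1 | 4.8% | 6.5 | 13% |
| 0.5 | 37.5 | 29.5 | 21% | 22.0 | 41% |
| 1.0 | 75 | 47.4 | 37% | 31.7 | 58% |

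Percentages come from unrounded counts. The arm size cancels from the shortfall, so 70 or 80 per arm gives the same percentages.

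**The case against.** There are four serious replies.

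**The information is not lost.** SAP 4.8.1 lists all adverse events by subject, SAEs have their own listing (Table 14.3.2.2), and Protocol 7.5 requires the AE listing to show treatment, SOC and preferred term. Event numbers by arm can be counted by hand. This stands. It means that no data are missing, but a by-subject listing is neither the summary by arm, SOC and preferred term that the protocol asks for nor the comparison with placebo that the endpoint names.

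**Table titles are not table shells.** SAP 7.1 gives titles without columns, and a title such as that of Table 14.3.1.1 does not exclude an event column. This stands in part. The point therefore concerns the rule taken literally. The rule covers any tabulation, however, and points against such a column.

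**Number of SAEs could mean number of subjects with SAEs.** This is hard to sustain. The subject-level SAE endpoint is listed separately, and Protocol 7.5 sets individual TEAEs beside participants in the same sentence.

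**The effect is small.** For rare SAEs it probably is, and safety is summarised descriptively. That limits the weight of the point without removing the mismatch.

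A reader might also infer that the SAE-number endpoint collapses into the SAE proportion, that repeat events vanish from the report, or that the contrast between arms is lost altogether. The documents support none of these. SAE types by arm are tabulated, every episode is listed, and the difference between arms in affected subjects is kept. Only the part of the contrast due to repeats, or to several terms within one SOC at the SOC row, is absent from the tables.

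**Conclusion.** The SAP's counting rule and the protocol's event-count commitments do not agree, and the departure is undeclared. Followed literally, the plan yields no by-arm number of individual TEAEs and no by-arm number of SAEs. The type half of the SAE endpoint, the primary safety endpoint and the SAE proportion are unaffected, as are the efficacy tests, alpha and power.

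The size in this trial cannot be derived from the documents. The percentages above rest on assumed rates and, in the clustered case, an assumed dispersion. They support only a direction: small where events are rare, as is likely for SAEs, and larger where the same event recurs, which is where the protocol's count of individual TEAEs adds most. This should be corrected before the SAP is final, as a matter of descriptive safety reporting.

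**What to change.** In SAP 4.8.1, limit the once-per-subject rule to the subject-incidence n (%) columns. Add an event-count column by treatment group, counting every episode, to Tables 14.3.1.1, 14.3.1.2 and 14.3.1.5, with the last two broken down by SOC and preferred term. If the sponsor prefers not to produce event counts, SAP 5 should say so and name the protocol summary and the endpoint component that are dropped.

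The cost is a sentence of SAP wording and one extra column in three tables already planned. The events are already recorded for the listings, so no new data collection is needed.
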